9.5 Data and Safety Monitoring Plan

The Principal Investigator will provide continuous monitoring of patient safety in this trial with periodic reporting to the Data and Safety Monitoring Committee (DSMC).

Meetings/teleconferences will be held at a frequency dependent on study accrual, and in consultation with the study Biostatistician. These meetings will include the investigators as well as study coordinators, data coordinator, regulatory associates, clinical data management associates, and any other relevant personnel the principal investigators may deem appropriate. At these meetings, the research team will discuss all issues relevant to study progress, including enrollment, safety, regulatory, data collection, etc.

The team will produce summaries or minutes of these meetings. These summaries will be available for inspection when requested by any of the regulatory bodies charged with the safety of human subjects and the integrity of data including, but not limited to, the oversight (Office of Human Research Ethics (OHRE) Biomedical IRB, the Oncology Protocol Review Committee (PRC) or the North Carolina TraCS Institute Data and Safety Monitoring Board (DSMB).

The UNC LCCC Data and Safety Monitoring Committee (DSMC) will review the study on a regular (quarterly to annually) basis, with the frequency of review based on risk and complexity as determined by the UNC Protocol Review Committee. The UNC PI will be responsible for submitting the following information for review: 1) safety and accrual data including the number of patients treated; 2) significant developments reported in the literature that may affect the safety of participants or the ethics of the study; 3) preliminary response data; and 4)

summaries of team meetings that have occurred since the last report. Findings of the DSMC review will be disseminated by memo to the UNC PI, PRC, and the UNC IRB and DSMB.

10.0 STATISTICAL CONSIDERATIONS

10.1 Study Design/Study Endpoints

This will be a prospective, single-arm, non-randomized, phase II study to examine the feasibility and acute and late toxicities of standard radiation treatment for unfavorable intermediate and high risk prostate cancer - this involves a combination of external beam radiation therapy and SBRT-CK and androgen deprivation therapy – while using advanced imaging modalities (PSMA/PET-mpMRI) to intelligently adapt the radiation fields. The radiation therapy usually takes 2 months and the follow up is 60 months, while the duration of the evaluation of the final results will be about 12 months after the end of treatment.

There is one primary endpoint:

(1) Late genitourinary toxicity and gastrointestinal toxicity at 12 months (these will be recorded at 1, 3, 6, 9, 12, 24, 36, 48 and 60 months after radiotherapy, according to CTCAE v5).

Table 1 shows an overview of late toxicities in randomized studies of conventionally fractionated schemes in primary prostate carcinoma. On average, the rate of late GI / GU toxicities of grade 2 or higher averaged a rate of approximately 16%.

Study	1 ³⁸	2 ³⁹	3 ⁴⁰	4^{41}	5 ⁴²	6 ⁴³				
Patient #	296	151	101	478	372	1065				
Total dose (Gy)	76	76	75.6	86.4	76	74				
Fractions #	38	38	42	39	38	37				
Dose/fraction (Gy)	2	2	1.8	2	2	2				
Late Reactions – RTOG G2+										
GI (%)	9	22.5	5.1	3.7	8	13.7				
GU (%)	19	13.4	16.5	15.5	24	9.2				

 Table 1 Summary of results from recent clinical trials with external beam radiotherapy.

Table 2 shows an overview of late toxicities in randomized studies of combination external beam radiotherapy and SBRT in primary prostate carcinoma. On average, the rate of late Grade 2 or higher GU toxicities is $\sim 11.4\%$ and for GI toxicities $\sim 6\%$.

Table 2 Summary of results from randomized	clinical	trials	treating	with	combination
external beam radiation therapy and SBRT.					

Study	1 ⁴⁴	2 ⁴⁵	3 ⁴⁶	4 ⁴⁷	5 ⁴⁸	6 ⁴⁹	7 ⁵⁰	8 ⁵¹
Patient #	121	26	76	39	108	48	41	45
EBRT dose (Gy)	45	44	46	45	45-50.4	45	45	45
EBRT Fractions #	25	20	23	25	25-28	25	25	25
CK dose (Gy)	21	18 or 21	18	21	19.5	19 or 21	21	18-21
CK Fractions #	3	3	3	3	3	2	3	3
		Late T	'oxicity –	Grade 2	+			
GI (%)	3.4	4.0	9.3	12.8	5.0	0.0	0.0	13.3
GU (%)	20.6	4.0	1.4	10.3	13.7	27.0	11.0	2.9

We denote p the probability that a patient experiences a late grade 2+ GU/GI toxicity. We want p to be small enough to claim the new imaging strategy (PSMA/PET-mpMRI) as feasible with no greater late toxicity. Specifically, the null and alternative hypotheses are:

$H_0: p \ge 0.30 \ vs \ H_1: p \le 0.15$

That is, we accept the claim that the new strategy is safe if the observed toxicity rate is not too high, and hope to reject the claim (H0) with sufficient power when the true toxicity rate is about 20%. With a sample size of 38, we reach 80% power to reject (if we observe ≤ 7 cases with late toxicity) the null hypothesis (H0) at alpha = 0.1. To account for 10% loss follow-up, we will enroll 42 patients to ensure 38 evaluable patients.

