Regarding nodal radiation, there are three published large randomized controlled trials looking at the role of pelvic nodal irradiation in nonmetastatic prostate cancer which have proved inconclusive.^{11–13} More recently, a randomized study conducted at a single institution in India (POP-RT, Murthy et al., JCO 2021) demonstrated improvements in biochemical failure free survival, disease free survival, and distant metastasis free survival with the addition of pelvic radiotherapy in patients with a nomogram-predicted risk of occult nodal metastasis exceeding 20%.¹⁴ There are two more trials currently underway (NCT01368588; PEACE 2 - GETUG - AFU 23) with estimated primary completion dates in 2025-2027.^{15,16} Collectively, these studies demonstrate the clinical equipoise in this area (whether or not to include nodes in the treatment field), which has been an area of intense debate for at least two decades (Nguyen & D'Amico, JCO 2008; Roach, JCO 2008).^{17,18}

Regarding defining intraprostatic lesions, ⁶⁸Ga-PSMA-PET alone has not been perfect. One meta-analysis found in seven studies that PSMA-expressing lesions were identified in only 203 of 273 patients (74%).¹⁹ However, this number appears to be confounded by lymph node detection rates. When looking at PSMA-PET defined DILs alone, the detection rates could be over 95%,²⁰ and may be even higher in high-risk disease which have greater PSMA-PET avidity.²¹ Three separate studies have shown that MRI and PSMA can deliver complimentary information on the localization of DILs.^{22–24} Therefore, it is likely PSMA PET-MRI is advantageous to PSMA PET-CT alone in identifying DILs. In a slice-by-slice analysis with histopathology, the sensitivity for PSMA PET alone, mpMRI alone, and PSMA PET-MRI combined, was 75%, 70%, and 82%, respectively for prostate cancer tumor detection. The specificity was 87%, 82%, and 67%, respectively.²⁵ Others have also found PSMA-PET/MRI to be superior to multiparametric MRI alone in detecting prostate cancer.²⁶

The concept of biological-guided (e.g. with PET) dose escalation (e.g. to DILs) is not new,²⁷ but has never been done with in combination with SBRT-CK. A feasibility study such as the current study under investigation will be the first step to investigating this question. Based on other studies, know that dose escalation in prostate cancer improves progression free survival.^{28,29}

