8.6 Assessment of Safety

All patients who received treatment (i.e. radiation) will be evaluated for toxicity at specified time points throughout the study; toxicity will be measured according to CTCAE version 5.0.

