10.2 Sample Size and Accrual

Accrual will take place at UNC. The design as proposed in the above section leads to 80% power at an alpha level of 10%. Taking into account that the dominant intraprostatic lesion (DIL, image-identified tumor in the prostate) can be safely defined in around 75% of the patients, and assuming a 10% patient drop-out (nonevaluable) rate, we will plan to enroll 42 patients in order to achieve the primary objective of this study. Based on a previous study conducted with a similar population, we anticipate averaged accrual of 2 patients per month, corresponding to 21 months to enroll 42 patients out of which we can accrue the 38 evaluable patients for this study.

Sequential boundaries will be used to suspend the trial if excessive grade 4 toxicity of any type, attributed to the treatment under study, is seen. If the study reaches a stopping boundary, it may be terminated by the PI, or submitted to the Data and Safety Monitoring Committee with a description of the failures to date and a rationale for why the study should be continued.

The accrual will be halted if the number of grade 4 toxicities is equal to or exceeds b_n out of n patients with full toxicity follow-up (see table below). This is a Pocock-type stopping boundary that assumes that a grade 4 toxicity rate of 0.05 is acceptable. If the true grade 4 toxicity rate is equal to 0.05, the probability of crossing the boundary is 0.20.

Number of Patients, n 1	2	3	4	5	6	7	8	9	10
Boundary, b _n 1	2	2	2	2	2	2	2	2	2
Number of Patients, n 11	l 12	13	14	15	16	17	18	19	20
Boundary, b _n 3	3	3	3	3	3	3	3	3	3
Number of Patients, n 21	1 22	23	24	25	26	27	28	29	30
Boundary, b _n 3	3	4	4	4	4	4	4	4	4
Number of Patients, n 31	1 32	33	34	35	36	37	38	39	40
Boundary, b _n 4	4	4	4	4	5	5	5		

In addition, grade 3+ toxicity (DLT) will also be monitored. The accrual will be halted if the number of grade 3+ DLTs is equal to or exceeds b_n out of n patients with full toxicity follow-up (see table below). This is a Pocock type stopping boundary that assumes that a DLT rate of 0.30 is acceptable. If the true DLT rate is equal to 0.30, the probability of crossing the boundary is 0.20.

Number of Patients, n 1	2	3	4	5	6	7	8	9	10
Boundary, bn -	-	3	4	4	4	5	5	6	6
Number of Patients, n 11	12	13	14	15	16	17	18	19	20
Boundary, b _n 7	7	7	8	8	9	9	9	10	10
Number of Patients, n 21	22	23	24	25	26	27	28	29	30
Boundary, bn 10	11	11	11	12	12	13	13	13	14
Number of Patients, n 31	32	33	34	35	36	37	38	39	40

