10.3 Data Analysis Plans

Analysis of primary endpoint, late toxicity rates, to decide whether to reject the null hypothesis, will be conducted as described above. In addition, the estimated acute and late toxicity rates will be reported with 95% confidence intervals in the final analysis.

As per the analyses of secondary outcomes, binary outcomes like (1) 2 and 5 years biochemical control according to the Phoenix criteria; (2) local recurrence rate after 2 and 5 years (defined by biopsy); and (3) rate of screened to truly included patients and compliance with dose restrictions, will be summarized by estimated proportions and associated 95% confidence intervals. Numerical outcomes like (4) quality of life (according to EPIC-26 and PCSI) will be summarized using descriptive (mean and standard deviation, median and range) statistics. Exploratory

correlation analyses will be conducted to identify biomarkers correlated with the diagnosis and the course of the disease, as well as gastrointestinal and urogenital toxicity.

In the event of an early termination of this study, the same analysis plan as described above will be followed, but based on the data available at the time of study termination.

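### Section 10 attaches adequate power to a true toxicity rate of about 20%, where the rule has 50% (80% holds at 15%), and credits the 42 with a DIL allowance it does not contain

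*Combined protocol and SAP*

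**What the plan says.** Section 10.1 defines p as the probability of a late grade 2+ GU/GI toxicity and sets H0: p ≥ 0.30 against H1: p ≤ 0.15. The explanation that follows says the investigators "hope to reject the claim (H0) with sufficient power when the true toxicity rate is about 20" per cent. The next sentence gives the design: "With a sample size of 38, we reach 80% power to reject" H0, with rejection at 7 or fewer cases and alpha = 0.1. It names no rate for the 80%. The enrolment figure comes next: "To account for 10% loss follow-up, we will enroll 42 patients to ensure 38 evaluable patients".

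Section 10.2 repeats the 80% power and 10% alpha, then accounts for the 42 differently. It says the number takes into account that the DIL "can be safely defined in around 75% of the patients", and continues: "assuming a 10% patient drop-out (nonevaluable) rate, we will plan to enroll 42 patients". It still expects 38 evaluable patients from the 42.

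Three other places bear on this:

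- Section 8.6: "All patients who received treatment (i.e. radiation) will be evaluated for toxicity".
- Section 2.3, on DILs defined by PSMA-PET: "the detection rates could be over 95" per cent.
- Section 10.3, on early termination: "the same analysis plan as described above will be followed", using the data then available.

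**The concern.** Two statements about the design do not match the design.

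**Power.** The formal alternative is 15%, but the prose puts the adequate power at about 20%. The only power figure in Section 10 is 80%, given in the very next sentence, so a reader will take it to apply at 20%. A reader who believes that will treat a failure to reject H0 as evidence that toxicity is above 20%. If power at 20% is really one half, that inference is unsound.

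**Enrolment.** Section 10.2 presents the 42 as the product of two allowances, while Section 10.1 derives the same 42 from one. If the 75% had been applied, the number would have to be larger. The clause also raises the question whether a patient without a defined DIL counts as evaluable, although Sections 8.6 and 10.1 imply that he does.

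The study is closing early, but Section 10.3 keeps the same analysis plan, so the final report will still draw on these statements.

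**Working it through.** **Inputs.** From Section 10.1: p0 = 0.30, p1 = 0.15, the 20% named in the prose, n = 38, rejection at X ≤ 7, alpha = 0.10, loss 10%, enrolment 42. From Section 10.2: DIL definable in 75%, drop-out 10%, enrolment 42. From Section 2.3: possible DIL detection of 95%.

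**1. Reproduce the plan's figures.** With X ~ Binomial(38, p), the probability of rejecting H0 is P(X ≤ 7 | 38, p).

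| True rate p | P(X ≤ 7) | Meaning |
|---|---|---|
| 0.30 | 0.0795 | exact alpha, within 0.10 |
| 0.15 | 0.7986 | the stated 80% |
| 0.16 | 0.7449 | power |
| 0.20 | 0.5003 | power |

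The stated 80% is reproduced at 15%. Solving P(X ≤ 7 | 38, p) = 0.80 gives p = 0.1497.

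**2. Can another cut-off or method give 80% at 20%?**

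- X ≤ 8 gives 0.655 at 20%, but its alpha is P(X ≤ 8 | 38, 0.30) = 0.152, above 0.10. So 7 is the largest admissible cut-off.
- The one-sample normal approximation with n = 38 gives power 0.529 at 20% (one-sided alpha 0.10) or 0.366 (two-sided).
- For comparison only: the smallest n with at least 80% exact power at 20% against 30%, with alpha ≤ 0.10, is 91 (X ≤ 21, alpha 0.090, power 0.808).

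So the 38 was not sized for 20%, and rounding or choice of method does not explain the gap.

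**3. Where the cut-off lies.** 7/38 = 18.4% rejects H0; 8/38 = 21.1% does not.

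**4. The 42.**

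| Allowance | Calculation | Result |
|---|---|---|
| 10% drop-out, by division | 38/0.90 | 42.2 |
| 10% drop-out, by multiplication | 38 × 1.1 | 41.8 |
| Drop-out and DIL at 75% | 38/(0.90 × 0.75) | 56.3 |
| Drop-out and DIL at 95% | 38/(0.90 × 0.95) | 44.4 |

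In the other direction, 42 × 0.90 = 37.8, close to the 38 expected, while 42 × 0.90 × 0.75 = 28.4. Only drop-out alone fits the 42. (Strict rounding up of 42.2 gives 43; a difference of one patient is not at issue.)

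**The case against.** The strongest reply on power is that the plan never literally states 80% power at 20%. The prose says only that power should be sufficient there, and the 80% sentence names no rate. The displayed hypotheses, n, cut-off, alpha and 80% all agree at 15%, so what remains is one loose phrase. That is right about the core design, which is sound at 15%. It does not rescue the phrase: no other power figure is offered, and 50% is not sufficient power on any reading.

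A second reply is that the test is against 30%, so non-rejection means only that 30% was not excluded, and that Section 10.3 also calls for 95% confidence intervals. At 8/38 the exact interval runs from about 9.6% to 37.3% and plainly includes 20%. This softens the consequence for a careful reader, but the sentence remains wrong.

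On the 42, it can be said that the plan never claims to have divided by 0.75, that no rule excludes patients without a DIL, and that the 95% is background rather than a planning input. All of that stands, and it is why no larger enrolment is called for. The text nevertheless says the 75% was taken into account, and it was not. This is the lesser of the two points.

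Two further replies are true but separate. Sections 2.1 and 4.1 define the primary endpoint as grade 3+, whereas the power statement concerns grade 2+. And if fewer than 38 patients are evaluable at closure, neither the planned power nor the alpha of a fixed cut-off of 7 still applies: P(X ≤ 7) at p = 0.30 is 0.28 for an illustrative n of 30. Both need their own resolution, and neither makes the present wording correct.

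**Conclusion.** Both parts hold. The rule of 7 or fewer in 38 has 80% power at a true late grade 2+ rate of 15% and 50% at the 20% the text names, a shortfall of 30 percentage points, with exact alpha 0.080. The 42 contains the 10% drop-out allowance and nothing for the DIL rate.

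These results rest on the exact binomial distribution, 38 evaluable patients and the one-sided reading that the hypotheses imply. They describe the planned trial; realised power depends on the number actually treated. The decision rule itself is not invalidated. These are clear errors of description that should be corrected.

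**What to change.** In Section 10.1, replace the reference to about 20% with 15%, and state the power as 80% at a true rate of 15% and 50% at 20%, with exact alpha 0.08.

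In Section 10.2, either delete the 75% DIL clause, or state that the 42 covers drop-out only and that the primary set is all irradiated evaluable patients whether or not a DIL is defined. A descriptive split of the primary rate by DIL defined or not could be added, but is optional.

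The cost is two restated sentences and a power statement that looks less favourable. There is no change to n, the cut-off, enrolment or data collection. The conflict between the grade 3+ primary endpoint and the grade 2+ rate used here must be reconciled separately.

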10.2 Sample Size and Accrual

Accrual will take place at UNC. The design as proposed in the above section leads to 80% power at an alpha level of 10%. Taking into account that the dominant intraprostatic lesion (DIL, image-identified tumor in the prostate) can be safely defined in around 75% of the patients, and assuming a 10% patient drop-out (nonevaluable) rate, we will plan to enroll 42 patients in order to achieve the primary objective of this study. Based on a previous study conducted with a similar population, we anticipate averaged accrual of 2 patients per month, corresponding to 21 months to enroll 42 patients out of which we can accrue the 38 evaluable patients for this study.

Sequential boundaries will be used to suspend the trial if excessive grade 4 toxicity of any type, attributed to the treatment under study, is seen. If the study reaches a stopping boundary, it may be terminated by the PI, or submitted to the Data and Safety Monitoring Committee with a description of the failures to date and a rationale for why the study should be continued.

The accrual will be halted if the number of grade 4 toxicities is equal to or exceeds b_n out of n patients with full toxicity follow-up (see table below). This is a Pocock-type stopping boundary that assumes that a grade 4 toxicity rate of 0.05 is acceptable. If the true grade 4 toxicity rate is equal to 0.05, the probability of crossing the boundary is 0.20.

Number of Patients, n 1	2	3	4	5	6	7	8	9	10
Boundary, b _n 1	2	2	2	2	2	2	2	2	2
Number of Patients, n 11	l 12	13	14	15	16	17	18	19	20
Boundary, b _n 3	3	3	3	3	3	3	3	3	3
Number of Patients, n 21	1 22	23	24	25	26	27	28	29	30
Boundary, b _n 3	3	4	4	4	4	4	4	4	4
Number of Patients, n 31	1 32	33	34	35	36	37	38	39	40
Boundary, b _n 4	4	4	4	4	5	5	5		

In addition, grade 3+ toxicity (DLT) will also be monitored. The accrual will be halted if the number of grade 3+ DLTs is equal to or exceeds b_n out of n patients with full toxicity follow-up (see table below). This is a Pocock type stopping boundary that assumes that a DLT rate of 0.30 is acceptable. If the true DLT rate is equal to 0.30, the probability of crossing the boundary is 0.20.

Number of Patients, n 1	2	3	4	5	6	7	8	9	10
Boundary, bn -	-	3	4	4	4	5	5	6	6
Number of Patients, n 11	12	13	14	15	16	17	18	19	20
Boundary, b _n 7	7	7	8	8	9	9	9	10	10
Number of Patients, n 21	22	23	24	25	26	27	28	29	30
Boundary, bn 10	11	11	11	12	12	13	13	13	14
Number of Patients, n 31	32	33	34	35	36	37	38	39	40
Boundary, b _n 14	14	15	15	15	15	16	17		

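### The only rule for declaring safety (7 or fewer late toxicities) is calibrated for 38 men, yet section 10.3 carries it to any early termination, with no cut-off for fewer men and no bar after a toxicity closure

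*Combined protocol and SAP*

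**What the plan says.** Section 10.1 sets the hypotheses as "H_0: p \ge 0.30 \ vs \ H_1: p \le 0.15", where p is the probability of late grade 2+ GU/GI toxicity. It describes the decision in words: "we accept the claim that the new strategy is safe if the observed toxicity rate is not too high". The one numerical rule is tied to a fixed number of men: "With a sample size of 38, we reach 80% power to reject (if we observe ≤ 7 cases with late toxicity"), at alpha 0.1.

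Section 10.2 repeats the operating characteristics: "The design as proposed in the above section leads to 80% power at an alpha level of 10" per cent. It then adds two accrual-halting tables, read patient by patient. For grade 4 toxicity: "If the true grade 4 toxicity rate is equal to 0.05, the probability of crossing the boundary is 0.20". For grade 3+ dose-limiting toxicity (DLT): "If the true DLT rate is equal to 0.30, the probability of crossing the boundary is 0.20". A crossing does not end the trial automatically. The principal investigator may terminate it, or refer it to the monitoring committee with a case for continuing.

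Section 10.3, on early termination: "the same analysis plan as described above will be followed, but based on the data available at the time of study termination". The summary of Amendment 6 says that this language was added because the study is closing early for low accrual and lack of funding.

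**The concern.** A count threshold controls error only at the sample size for which it was computed. Seven events is about 18% of 38 men (7/38) but 70% of 10 men. If the same count is carried to a shorter trial, the safety claim becomes easier to reach the earlier the trial stops.

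One permitted reason for stopping early is excess toxicity. The plan does not say whether a trial closed at a boundary may still be declared safe, and the only analysis it offers for that case is the one built on the count of 7. The primary objective is to determine safety, so a reading under which a toxicity closure makes the safe conclusion more likely should not be left open. The gap also matters for closure on accrual grounds, which is the situation Amendment 6 describes.

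**Working it through.** **Inputs.** Section 10.1: null rate 0.30, alternative rate 0.15, 38 evaluable men, pass if 7 or fewer late events, alpha 0.10. Section 10.2: the grade 4 boundary is 1 at n=1, 2 for n=2–10, 3 for n=11–22, 4 for n=23–35 and 5 for n=36–38; the DLT boundary runs from 3 at n=3 to 17 at n=38.

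**Step 1: the plan's figures.** With P(X≤7 | n, p) = Σ C(n,k) p^k (1−p)^(n−k) over k = 0 to 7:
- Power at n=38, p=0.15: 0.7986, the printed 80%.
- Alpha at n=38, p=0.30: 0.0795, inside the stated 0.10. A cut-off of 8 would give 0.152.
- Crossing probability by exact patient-by-patient recursion: 0.195 for grade 4 at 0.05 and 0.206 for DLT at 0.30. Both match the printed 0.20.

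**Step 2: the same count on fewer men, p=0.30.** For n=10, 1 − [45(0.3⁸)(0.7²) + 10(0.3⁹)(0.7) + 0.3¹⁰] = 1 − 0.0016 = 0.998.

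| Men analysed | P(7 or fewer), p=0.30 |
|---|---|
| 7 | 1.000 |
| 10 | 0.998 |
| 20 | 0.772 |
| 30 | 0.281 |
| 38 | 0.079 |

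**Step 3: with the boundaries, upper case.** Assumptions: every crossing ends the trial; the count of 7 is applied to the men accrued at that point; grade 4 events are among the DLTs; late toxicity is independent of the monitored toxicity; late rate 0.30. False-safe = P(no halt) × 0.0795 + Σ P(halt at n) × P(X≤7 | n, 0.30).
- Grade 4 at 0.05, DLT at 0.10: (1 − 0.195) × 0.0795 + 0.163 = 0.064 + 0.163 = 0.227.
- Grade 4 at 0.05, DLT at 0.30: (1 − 0.330) × 0.0795 + 0.277 = 0.053 + 0.277 = 0.330.

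**Step 4: exact cut-off at the actual n.** Replace 7 by the largest c with P(X≤c | n, 0.30) ≤ 0.10. Under the same assumptions the false-safe probability is 0.064 + 0.007 = 0.071 in the first case and 0.053 + 0.012 = 0.065 in the second.

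**Step 5: men enrolled but not yet fully followed at the halt.** If 14 further men are already enrolled and are counted (total capped at 38), the first case falls from 0.23 to 0.17. With 24 further men it falls to 0.11. At the planned 2 men a month, these are 7 and 12 months of accrual.

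**Step 6: the opposite reading.** If every halt is final and bars the safety claim, power at a late rate of 0.15 is P(no halt) × 0.7986:
- Grade 4 at 0.05, DLT at 0.10: 0.805 × 0.7986 = 0.64.
- Grade 4 at 0.05, DLT at 0.30: 0.670 × 0.7986 = 0.53.
- Grade 4 at 0.02, DLT at 0.10 (assumed lower rates): 0.959 × 0.7986 = 0.77.

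Alpha then falls to 0.064 and 0.053 in the first two cases. With both rates at their tolerated limits, the chance of crossing at least one boundary is 0.33 with grade 4 nested in DLT, or 0.36 if the two are independent.

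**The case against.** The strongest defence is that nothing printed is miscalculated. Section 10.2 attaches 80% and 10% to the design of the preceding section, which is the single-stage late-toxicity test, and it discloses each crossing probability separately. That is correct.

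A reader might infer that the boundaries cut the trial's power to 53–64%. The documents do not support this. Crossing suspends accrual pending a decision by the principal investigator or the committee. The rates 0.05 and 0.30 are called acceptable, not expected. At grade 4 0.02 and DLT 0.10 the loss is about 3 points. Power is lost only if a halt bars the safety claim; if the count of 7 is applied despite a halt, power is not reduced (0.83 to 0.86 in the two cases of step 3). The power loss and the inflated false-safe rate therefore belong to alternative readings and cannot both be charged to the plan.

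A reader might also point to a high DLT rate combined with a late rate of 0.15, where a halted trial would nearly always pass. That is not an error for the primary endpoint, because 0.15 lies within the alternative and DLTs are acute events with their own monitoring.

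Finally, the same analysis plan could mean testing the null of 0.30 at alpha 0.10 on the men available, which keeps the error near 0.07. This is a fair reading, but the text gives no cut-off other than 7 and does not choose between the readings. That the clause was written for low accrual explains its origin but does not limit its scope: it covers any early termination, and the missing cut-off matters for an accrual closure too.

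**Conclusion.** The point holds as a gap in the decision rule, not as an arithmetic error. The count of 7 is valid at 38 men. Below that the plan has no stated cut-off, and it does not say what may be claimed after a toxicity closure. Read literally, the rule cannot fail at 7 men and has a 77% chance of passing at 20 men when the late rate is the unacceptable 0.30.

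The 0.23 to 0.33 false-safe figure, against the stated 0.10, is an upper case. It rests on binding boundaries, monitored toxicity at the stated rates, independence of late and monitored toxicity, and no further follow-up of men already enrolled. Relaxing any one of the first, second or fourth lowers it.

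The arithmetic does not depend on which toxicity grade p counts. Three separate inconsistencies bear on the same sections and need reconciling: the primary endpoint is grade 3+ in section 4.1 but p is grade 2+ in section 10.1; section 10.1 also speaks of rejecting "with sufficient power when the true toxicity rate is about 20" per cent, where the rule has power of only 0.50; and sections 6.4 and 7.1.4 state a plain 30% DLT halting rule that differs from the table in section 10.2.

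**What to change.** In sections 10.1 to 10.3:

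1. State that the safety claim requires 7 or fewer late events in 38 evaluable men and no permanent closure for toxicity.
2. After a toxicity closure, report the toxicity rates with exact confidence intervals and make no safety claim.
3. After closure for any other reason, replace the count of 7 with the exact binomial test of p ≥ 0.30 at alpha 0.10 for the number actually evaluable, or report exact intervals only.
4. Label 80% power and 10% alpha as belonging to the late-toxicity test without the monitoring boundaries.
5. Optionally add, marked as a worst case with binding boundaries, a joint halting probability of about 0.33–0.36 with both rates at their tolerated limits, and power of about 53–64% with grade 4 at 0.05 and DLT at 0.30 or 0.10, alongside about 77% at grade 4 0.02 and DLT 0.10. The 53–64% should not be presented as the trial's power.

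The cost is a few sentences. The boundaries, the monitoring and the 42 patients are unchanged. The one real concession is that a trial closed early gives up a safety claim that the current wording might have allowed.
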